### **Number of Sites/Investigators/Patients**

There will be up to a total of twenty two (22) sites enrolling patients, all of which are familiar with randomized clinical trials and are part of the Major Extremity Research Consortium (METRC). Approval by each center's institutional review board will be obtained prior to commencing the study and we will follow the research guidelines set forth by each site. A total 50 patients will be enrolled in this study. The definitive treatment of the tibia fracture in all patients must be with an intramedullary nail. The number of patients enrolled at each site will be dependant on the random nature of the admission to hospital of eligible patients. No one site will enroll more than 10 patients in this study.

The randomization scheme is a central, computerized process using a web based, distributed data collection system. A block randomization scheme with no subgroups will be used for each center participating in the trial. Blocks will use randomly permuted sizes of even numbers only, consisting of an equal number of treatments in each block. The order of the treatment assignments in each block is random. Along with treatment allocation, each patient randomized is assigned an individual study number.

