### **Statistical Analyses/Data Presentation**

### Sample Size Justification

To address our primary objective, a comparison of healing rates between BMP and Autogenous Bone Grafts, we assume at 20% higher healing rate in BMP treated patients ( Jones et al, 2006), with a baseline healing rate of 65% (with autogenous bone graft). Stipulating a study power of 80% and an alpha level=0.05, and a non-inferiority margin of 20% our study will require at least 14 patients per treatment arm. If we stipulate our non-inferiority margin to be 10%, we will require 25 patients per group. Thus, to be most conservative, our study will recruit 50 patients total (25 patients per treatment arm). We will complete an interim evaluation of results once 25 patients have been enrolled, including a power analysis.

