### Final Analysis

The results will be reported comparing the outcomes in the groups at each follow-up period. It is anticipated that the required patients will be entered into the investigation during an 18-month period and will be followed for one year. Thus, the data collection time will be a 2.5- year period. We believe that at that time, the results of the study will reveal whether any differences exist with this high-energy disabling fracture in terms of outcomes, union rates, times to union, soft-tissue complications and infection rates.

Data will be analyzed on an intent to treat basis (patient data included in the treatment group and stratum to which randomized). Fishers exact test will be used to compare categorical variable and the Student t test will be used for continuous variables for comparisons between the two groups.

Quality of life data will be coded and scored according to the guidelines provided with the SMFA (Coding Key Manual, Musculoskeletal Function Assessment, Injury and Arthritis Survey) and the SF-12 (Coding Manual for the SF-12 Health Survey).

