### Steps to Minimize Risk

There may be unknown risks/discomforts involved. Study staff will update the participant's in a timely way on any new information that may affect the patient's health, welfare, or decision to stay in this study. The risks of participation in this study if one is randomized to the Rh-BMP 2 group are documented from previous studies. If there is an accelerated healing rate in those patients who receive rhBMP-2 versus the autograft, the patient benefits may include less pain, a decrease in the need for secondary interventions, and improved functional outcome. If there is no healing with the use of the Rh-BMP 2 group, the patient will still be able to receive autograft to promote healing.

The patient's physician and the study investigators will share responsibility for patient safety. They will ensure patient confidentiality throughout trial management. The investigator and designated study staff will be responsible for adhering to institutional standards for ensuring patient safety and confidentiality.

At each clinical visit, assessment will be made based on vital signs, physical evaluation of the limb including skin inspection, pain, swelling, infection, neurovascular status and radiographic evaluation of the involved tibia. There will be close monitoring of the occurrences of adverse events. In addition, certain vulnerable patient populations have been excluded from this study.

Every effort will be made to keep patient information confidential.

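### The trial is sized for non-inferiority but analysed by intent to treat alone; if rhBMP-2 is truly worse, receipt of autograft in that arm raises the risk of a false non-inferiority claim

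*Combined protocol and SAP*

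**What the plan says.** The Sample Size Justification frames the primary comparison as non-inferiority. It takes 65% healing with autograft and says "we assume at 20% higher healing rate in BMP treated patients". It continues "Stipulating a study power of 80% and an alpha level=0.05", then gives two sizes: "a non-inferiority margin of 20% our study will require at least 14 patients per treatment arm", and "If we stipulate our non-inferiority margin to be 10%, we will require 25 patients per group". The second gives the recruited total of 50.

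The Final Analysis section then says "Data will be analyzed on an intent to treat basis", with Fisher's exact test for categorical outcomes. It names no per-protocol set, no sensitivity analysis for departures from the allocated graft, and no confidence limit to set against a margin. The null hypothesis under Research Question is equality of union rates.

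Steps to Minimize Risk says that if rhBMP-2 does not produce healing, "the patient will still be able to receive autograft to promote healing". The Retrieval Study section likewise names autograft as the salvage. Neither section says how union reached after salvage is scored at 12 months, the time point of the primary outcome.

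**The concern.** Intent to treat is the cautious choice for a superiority claim because mixing the treatments shrinks the observed difference. For non-inferiority the same shrinkage can work in favour of the claim. If rhBMP-2 heals fewer fractures than autograft, each patient in that arm who ends up with the autograft outcome moves the observed difference towards zero and away from the margin. A conclusion that rhBMP-2 is not unacceptably worse could then partly reflect the autograft given in its arm.

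There are two routes. One is crossover: a patient allocated rhBMP-2 receives autograft instead. The other is salvage: the allocated graft fails, autograft follows, and the later union is credited to rhBMP-2.

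**Working it through.** **1. Reproduce the plan's sample size.** Inputs from the Sample Size Justification: autograft 0.65; rhBMP-2 0.85 (reading the 20% as absolute); power 80%; alpha 0.05; margin m of 0.20 or 0.10. Allocation is 1:1, since blocks are described as "consisting of an equal number of treatments in each block". With unpooled variance and one-sided alpha,

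n per arm = (0.65×0.35 + 0.85×0.15) × (1.645 + 0.842)² / (0.20 + m)²

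- m = 0.20: 0.355 × 6.183 / 0.16 = 13.7, so 14
- m = 0.10: 0.355 × 6.183 / 0.09 = 24.4, so 25

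Both stated figures are reproduced. Sidedness is not stated; one-sided 0.05 is inferred from this match (one-sided 0.025 would give 18 and 31). A superiority design for 65% against 85% would need 73 per arm at two-sided 0.05, so 50 in total is a non-inferiority size.

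**2. False non-inferiority rate under crossover.** Let rhBMP-2 be worse by exactly the margin, and let a fraction x of its arm have the autograft outcome. The documents give no departure rate; x is assumed.

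- p₂ = (0.65 − m) + x·m
- SE = √[(0.65×0.35 + p₂(1 − p₂)) / 25]
- false-claim rate = Φ[(p₂ − 0.65 + m)/SE − 1.645]

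Worked case, m = 0.10 and x = 0.20: p₂ = 0.57, SE = 0.1375, 0.02/0.1375 = 0.145, and Φ(0.145 − 1.645) = 0.067.

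| x (assumed) | 10-point margin | 20-point margin |
|---|---|---|
| 0 | 5.0% | 5.0% |
| 12% (3 of 25) | 6.0% | 7.1% |
| 20% (5 of 25) | 6.7% | 8.8% |
| 30% | 7.7% | 11.3% |

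**3. Salvage counted as success.** Assume a fraction s of rhBMP-2 failures have salvage autograft, 65% of those heal and are scored as united by 12 months, and controls have no such gain. Then p₂ = p + (1 − p) × s × 0.65, where p = 0.65 − m. At m = 0.10, p = 0.55:

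- s = 0.25: p₂ = 0.55 + 0.45×0.25×0.65 = 0.623; false-claim rate about 13%
- s = 0.50: p₂ = 0.55 + 0.45×0.50×0.65 = 0.696; false-claim rate about 29%

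At the 20-point margin the corresponding rates are about 16% and 37%.

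**4. The opposite case.** At the plan's own 65% against 85%, crossover gives p₂ = 0.85 − 0.20x. At the 10-point margin the chance of claiming non-inferiority falls from 81% (x = 0) to 73%, 68% and 61% for x = 12%, 20% and 30%.

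**5. Power in a smaller per-protocol set.** At 65% against 85% and the 10-point margin, power = Φ[0.30/√(0.355/n) − 1.645]: 81% for n = 25, 76% for n = 22, 73% for n = 20.

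**The case against.** A reader might infer that departures always favour a non-inferiority claim. They do not. At the plan's own assumption that rhBMP-2 is 20 points better, mixing the grafts makes the claim harder to reach (step 4).

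A reader might also infer that any off-protocol patient makes the arms more alike. Only receiving the other graft, or sharing its outcome, does that. A patient grafted late may simply heal less often. If 20% of the rhBMP-2 arm healed at 40% and the rest at 55% (assumed), p₂ = 0.8×0.55 + 0.2×0.40 = 0.52 and the false-claim rate is about 3%, below nominal.

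The salvage passages should not be read as evidence of crossover: they describe autograft after rhBMP-2 has failed. Their relevance is the unstated scoring of later union. Need for further intervention is listed as an outcome under Measurements, but nothing says that it makes the primary outcome a failure.

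The graft is a single surgical implant, so drug-style non-adherence does not apply, and the documents give no crossover rate. The simple crossover effect at the 10-point margin is modest, at 1.0 to 2.7 percentage points.

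Finally, the Final Analysis section specifies no non-inferiority test, so the claim at risk is not yet a planned output. That is a fair point and a gap in its own right. It shapes the fix but does not remove the concern: once a limit is compared with a margin, the analysis set and the scoring of salvage still have to be fixed.

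**Conclusion.** The concern holds as a type I error point and is a cheap improvement rather than a fatal flaw. It rests on two facts in the plan: a non-inferiority sample size, and intent to treat as the only analysis set. Its size depends on assumed rates. Crossover alone moves the false-claim rate from 5.0% to between 6.0% and 7.7% at the 10-point margin for 12% to 30% departures. The larger figures, about 13% and 29%, arise only if healing after salvage is scored as union, under assumed salvage and healing rates and no matching gain in controls. All rates take one-sided 5% and 25 per arm.

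The documents do not support saying that intent to treat is wrong here, or that it will produce a false claim. It should stay, but should not stand alone.

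**What to change.** In the Final Analysis section, for 12-month union:

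- State that the lower confidence limit of the difference (rhBMP-2 minus autograft) will be compared with the 10-point margin that set the sample size of 50, and state the sidedness.
- Keep intent to treat. Add a per-protocol analysis limited to patients who met the inclusion and exclusion criteria, received the allocated graft within the protocol's window, had no other healing procedure listed among the exclusions, and have an adjudicated 12-month outcome.
- In both sets and both arms, count union reached only after a further grafting procedure as not healed on the allocated graft. The exclusion list does not name repeat grafting, so the per-protocol definition alone would not close the salvage route.
- Claim non-inferiority only if the limit clears the margin in both sets, and report any disagreement.

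The cost is one further pre-specified analysis and a wider interval in the smaller set: power of about 76% with 22 per arm or 73% with 20, against 81% with 25. Requiring both sets to succeed cannot raise these figures. To keep 25 per-protocol patients per arm, recruitment would be 27, 28 or 32 per arm if 5%, 10% or 20% fell out (25/0.95, 25/0.90, 25/0.80, rounded up; assumed rates). A per-protocol set is not fully protected by randomisation, which is why agreement of both sets is required rather than a switch from one to the other.

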## **IRB00003098 Funding Protocol rhBMP-2/ACS vs. Autograft for Critical Size Tibial Defects**

*Null hypothesis: rhBMP-2/ACS has the same union rate when used in critical-sized defects as does ICBG.*

*Secondary:*

What is the relative effect of rhBMP-2 versus autogenous ICBG on infection rates in patients with nonunion or critical size defects following tibial shaft fractures?

*Null hypothesis #2: The infection rate in open tibias with critical-sized defects treated with rhBMP-2 and autogenous ICBG are the same.*

What is the economic impact of the use of RhBMP 2 for tibial fractures with critical sized defects?

*Null hypothesis #3: There will be no difference in the economic cost of the treatment of critical sized defects using the RhBMP-2 versus iliac crest bone graft.*

This investigation is a prospective, stratified, parallel, randomized, blinded multicenter trial to evaluate the use of rhBMP-2/ACS in 25 patients versus a control group of 25 patients who have tibial fractures with critical size defects. A committee of orthopaedic surgeons will independently adjudicate our primary outcome, fracture healing at 12 months. Participating centers are part of the Major Extremity Research Consortium (METRC) and have experience with performing randomized clinical trials. Approval by each center's institutional review board will be obtained prior to commencing the study and we will follow the research guidelines set forth by each site.

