## **IRB00003098 Funding Protocol rhBMP-2/ACS vs. Autograft for Critical Size Tibial Defects**

weeks of injury, the patient will not be eligible to participate. The literature supports interventions for non union be considered after 6 months from injury. This will guard against enrolling patients with “non-unions”. Patients eligible for this study all had open fractures with bone defects. The soft tissue envelope needs to adequately recover from the original injury to be safe for additional surgery. Extending the window until 16 weeks permits time for adequate soft tissue recovery for the surgical procedures.

The case report form provides a space to record the size of the defect as measured from the AP and lateral x-rays. The measurement should be recorded as a total of the length, width and depth of the defect. Because an intramedullary nail is in place, the depth of the defect is to be recorded as the cortical thickness. In addition, there should be measurements made of the defect volume intra-operatively. The extent of the intra-operative defect will include area of bone loss >25% of the circumference to avoid measurement of small spikes that are clinically irrelevant. Intra-operative defect size will be recorded on case report forms.

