### **Inclusion/Exculsion Criteria**

#### Criteria For Inclusion Of Subjects:

- Patients 18-65 years old with an open tibia fracture involving diaphysis (if patient has a bilateral tibia fracture and both require a bone graft, then each will be randomized separately).
- Tibia fractures with a circumferential bone defect of at least one centimeter in length compromising at least 50% of the circumference of the bone.
- The definitive treatment of the tibia fracture must be with an intramedullary nail (may have temporary external fixation prior to IM nail placement).
- Patients whose treatment plan includes placement of a bone graft between 6 to 16 weeks after their initial injury.
- Patients who have no evidence of infection by clinical examination (defined as active infection at the operative site, purulent drainage from the fracture or evidence of active osteomyelitis at the time of bone graft).
- Patients who are independent in living and ambulation prior to injury.
- Patients who are English speaking.
- Patients who are willing to provide consent and available for follow-up for at least 12 months following definitive surgical procedure.

Criteria For Exclusion Of Subjects:

- Patients who are pregnant or lactating.
- Patients with known hypersensitivity to rhBMP-2 or bovine type I collagen.
- Patients with a history of tumor, a resected or extant tumor, an active malignancy, or patients undergoing treatment for malignancy.
- Patients who are skeletally immature (<18 years of age or no radiographic evidence of epiphyseal closure).
- Patients with inadequate neurovascular status, e.g. high risk of amputation.
- Patients with compartment syndrome of the affected limb.
- Patients with immune deficiency or history of auto-immune disease,
- Patients who have undergone treatment of any other investigational therapy within the month preceding implantation or planned within the 12 months following implantation.
- Patients unable to return for required follow-up visits.
- Patients who have medical co-morbidities that preclude treatment with a general anesthetic.
- Patient who is pending incarceration or who is incarcerated.
- Patients with an active infection at the operative site defined clinically by skin changes including redness, warmth and active draining, purulent drainage from the fracture or evidence of active osteomyelitis based on radiographic evidence of lytic lesions at the time of bone grafting.

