- Patient has segmental defects longer than 5cm in length as measured on AP and lateral radiographs of the injury taken after the final debridement following internal fixation
- Patient has a segmental defect longer than 6cm as measured intraoperatively after debriding .
- Patients who have segmental defects that require more than 60 cc of bone graft.
- Patients who require more than one large kit of rhBMP-2 at time of surgery.
- Patient's anticipated treatment plan also includes the use of other procedures to promote fracture healing, e.g. ultrasound, magnetic field or electrical stimulation.
- Patient's tibia fracture has been treated with additional fixation beyond the intramedullary nail, e.g. plates, wires or screws, and additional surgical fixation, e.g. fibulectomy, exchange nail and dynamization of locked nail
- Patients who have pathological fractures; a known history of Paget's disease or known history of heterotopic calcification.
- Patients with a Glasgow Coma Scale less than 15 (less than fully awake) at the time of informed consent.
- Patients with previous hardware in place that prevents placement of an intramedullary nail for treatment of the tibial shaft fracture.
- Patients with prior use of INFUSE.

*If the patient is a female of child bearing potential:*

- Does she have a negative pregnancy test (administered within 72 hours prior to surgery)?
- Has she agreed to use adequate contraception for a period of at least 1 year following implementation of rhBMP-2?

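### Pre-graft radiographic defect size is recorded but used neither in randomisation nor in the union comparison, which gives up modest precision if defect size predicts union

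*Combined protocol and SAP*

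**What the plan says.** - **Outcome.** The study description following the research questions states: "A committee of orthopaedic surgeons will independently adjudicate our primary outcome, fracture healing at 12 months". The outcome is binary.
- **Entry limits on defect size.** The inclusion list requires "Tibia fractures with a circumferential bone defect of at least one centimeter in length compromising at least 50% of the circumference of the bone". The exclusion list rules out anyone where "Patient has segmental defects longer than 5cm in length as measured on AP and lateral radiographs of the injury taken after the final debridement", and sets further limits of 6 cm measured at surgery and 60 cc of graft.
- **Recording.** The Protocol section says: "The case report form provides a space to record the size of the defect as measured from the AP and lateral x-rays". It asks for a total of length, width and depth, and for a separate intra-operative measurement.
- **Randomisation.** Number of Sites/Investigators/Patients says: "A block randomization scheme with no subgroups will be used for each center participating in the trial".
- **Analysis.** Final Analysis states: "Fishers exact test will be used to compare categorical variable and the Student t test will be used for continuous variables". No covariate, stratified union analysis or sensitivity analysis appears anywhere.
- **Strata.** The design is called stratified, and Final Analysis says "Data will be analyzed on an intent to treat basis (patient data included in the treatment group and stratum to which randomized". No stratum is defined. Centre is the only factor described in the allocation scheme, and nothing ties a stratum to defect size.

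**The concern.** Defect size defines the population, and the radiographic length is fixed before the staged graft. It is therefore the obvious candidate for a prognostic baseline variable. Blocking within centre does not balance it, particularly as "There will be up to a total of twenty two (22) sites enrolling patients" for 50 patients, which will leave many blocks incomplete.

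If longer defects unite less often, two things follow from an unadjusted comparison. The interval for the union difference is somewhat wider than it need be. And if the arms differ by chance in mean length, readers will ask how much of the observed difference reflects that. An adjustment chosen only after the imbalance has been seen would look selective, so it has to be written down beforehand.

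**Working it through.** **Inputs from Sample Size Justification.** Control union 65%; 20% higher with rhBMP-2, read as 85%; power 80%; alpha 0.05; margins 20% and 10%; 25 per arm.

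**The plan's own figure.** With one-sided alpha 0.05 and unpooled variance,
n = (1.645 + 0.842)² × (0.65×0.35 + 0.85×0.15) / (0.20 + margin)².
- Margin 0.10: 6.18 × 0.355 / 0.09 = 24.4, so 25.
- Margin 0.20: 6.18 × 0.355 / 0.16 = 13.7, so 14.

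Both stated sizes reproduce. One-sided 0.025 gives 31 and 18, which do not match.

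**Assumptions not in the documents.** Length is uniform on 1 to 5 cm. The odds of union fall 1.5-, 2- or 3-fold per extra cm in both arms, with overall rates held at 65% and 85%.

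**Standard error of the unadjusted difference.** √(0.355/25) = √0.0142 = 0.119, about 12 points.

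**Chance imbalance in length.**
- SD = 4/√12 = 1.155 cm.
- SE of the difference in means = 1.155 × √(2/25) = 0.327 cm.
- P(|difference| > 0.5 cm): z = 0.5/0.327 = 1.53, two-sided probability about 13%.

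**Effect of a 0.5 cm imbalance.** Averaged over the arms, it moves the observed union difference by 3.5, 5.5 or 7.7 points in the three scenarios, that is 7.0, 11.0 or 15.4 points per cm.

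**Gain from adjustment.** Simulated trials of 25 v 25 compared the unadjusted difference with a logistic model on arm and length, standardised to a risk difference. Extra patients = 50 × (1/ratio − 1).

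| Fall in odds per cm | Variance ratio, adjusted/unadjusted | Variance cut | Worth on 50 patients |
|---|---|---|---|
| none | about 1.02 | 2% loss | about −1 |
| 1.5-fold | 0.98 | 2% | about 1 |
| 2-fold | 0.93 | 7% | about 4 |
| 3-fold | 0.83 | 17% | about 10 |

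**Cross-check by hand.** The share of variance due to length imbalance is (slope × 0.327)² / 0.0142:
- (0.070 × 0.327)² / 0.0142 = 3.7%
- (0.110 × 0.327)² / 0.0142 = 9.1%
- (0.154 × 0.327)² / 0.0142 = 17.9%

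Multiplying what remains by 1.02, the cost of estimating one slope, gives 0.98, 0.93 and 0.84, in line with the table. A separate simulation with a linear model gave 0.97, 0.92 and 0.85 at odds ratios per cm of 0.61, 0.47 and 0.37.

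**Power.** In that linear-model simulation, approximate power for the 10-point margin (one-sided 0.05) was 80–81% unadjusted. Adjusted, it ran from 80% with no relation to 85% at an odds ratio of 0.37.

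**How many covariates.** Expected non-unions are 25×0.35 + 25×0.15 = 12.5, so a single covariate is prudent.

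**The case against.** An unadjusted primary test is a defensible choice in a randomised trial of 50, and several points against adjustment have force.

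- **Prognostic strength is unknown.** The documents do not quantify it. A reader might infer from the term critical size and from the entry limits that length must be prognostic within 1 to 5 cm. The documents do not show this: the 60 cc and one-kit limits read partly as product limits, and the entry criteria already narrow the range. With lengths skewed toward 1 cm (SD 0.78 cm), simulated variance ratios were only about 1.00, 0.97 and 0.89. This stands, and it is why the gain is given as a range that includes a small loss.
- **Imbalance is not bias.** A reader might infer that chance imbalance in defect size biases the primary result, or uses up most of the 10-point margin. Neither follows. Randomisation keeps the unadjusted comparison unbiased and its type I error valid. The 3.5- to 7.7-point shifts are conditional on a 0.5 cm imbalance, and that variation is already inside the 12-point standard error.
- **The model can fail.** If every rhBMP-2 fracture unites (0.85²⁵ = 1.7%), the arm coefficient has no finite estimate. Where the model converged, delta-method 95% intervals covered about 93–94% in simulation. Both points call for extra wording in the plan, not for dropping the adjustment.
- **The length value may not be a separate field.** The Protocol section asks for a total of length, width and depth, so a stand-alone length is inferred from the 5 cm exclusion. Providing a space on the form also does not guarantee completion for every patient. This stands and is handled in the fix.

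**Conclusion.** The point holds as a modest, inexpensive improvement. The documents show a pre-graft size measurement that enters neither the allocation nor the union comparison. Under the stated assumptions, adjusting for length would cut the variance by about 2% to 17%, worth roughly 1 to 10 patients on 50, and would cost about 2% if length does not matter. Pre-specification also settles in advance how any visible imbalance in defect size will be handled.

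A reader might infer that adjustment would rescue the trial's power. It would not: the gain for the 10-point margin is at most a few percentage points. The separate mismatch between non-inferiority sizing and Fisher's test of equality is a different matter, which a covariate does not resolve.

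**What to change.** In Final Analysis, define the primary union estimate as a risk difference with 95% CI, adjusted for pre-graft radiographic defect length, using logistic regression on arm and length standardised to a risk difference. Specify that:
- length is the measurement used for the 5 cm exclusion, entered as its own value; it is neither the length-width-depth total nor the intra-operative size, which is measured by a surgeon who may know the allocation;
- length is the only covariate, and the interval method is named;
- under separation, the fallback is Firth penalised logistic regression or a Mantel-Haenszel risk difference over two length strata fixed in advance;
- the unadjusted comparison is reported as a sensitivity analysis.

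The cost is a few sentences in the plan, slightly more analysis work, and a check that the case report form holds length as a separate, completed field. No extra patients or visits are needed. The statistical downside is the roughly 2% variance loss if length is not prognostic. The wording should be fixed before any outcome data are seen, including at the interim evaluation planned once 25 patients are enrolled.

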## **Measurements**

Effectiveness Evaluation (x-ray, weight bearing, 2nd procedures)

Outcome measures will be “radiographic union,” “clinical union”, “wound healing and infection,” and “need for further intervention.”

Pain-will be documented using the Visual Analogue Scale (VAS) at each visit.

Short Form-12 (SF-12), Short Musculoskeletal Functional Assessment (SMFA) will be completed at 6 months and 12 months.

The **SF-12** questionnaire was developed from the Medical Outcomes Study. It is a self-administered, 12-item questionnaire that measures health-related quality of life in 8 domains. Both physical and mental summary scores can be obtained. Each domain is scored separately from 0 (lowest level) to 100 (highest level). The instrument has been extensively validated and has demonstrated good construct validity, high internal consistency, and high test-retest reliability. Our decision to use the SF-12 over other available instruments was based on its widespread use in orthopaedics, its use in previous studies evaluating fracture outcomes, and the strong evidence of validity.

The **SMFA** is a shorter version of the 101 item Musculoskeletal Function Assessment (MFA) questionnaire. The SMFA is a 46 item questionnaire consisting of the dysfunction and bother index. The dysfunction index has 34 items for assessment of patient function, while the bother index consists of 12 items designed to detect how much patients are bothered by functional items. The SMFA has been evaluated for reliability, validity and responsiveness in patient populations. We chose this scale because it is a short, validated instrument to provide us with information regarding the patient’s functional status.

Safety Evaluation (complications, re-operations, adverse events)

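### Fisher's exact test is valid for the binary outcomes but gives away power at about 25 per arm; Boschloo's exact test keeps error within 5% and never has lower power

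*Combined protocol and SAP*

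**What the plan says.** The Final Analysis section names one method for categorical data: "Fishers exact test will be used to compare categorical variable". It gives no sidedness, no mid-P or unconditional version, and no separate method for union.

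Several outcomes reach this test as two-group yes/no comparisons. The Research Question section sets null hypotheses of equal union rates and equal infection rates. Measurements adds clinical union and "need for further intervention", and Final Analysis adds soft-tissue complications.

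On size and error rate, Sample Size Justification says "our study will recruit 50 patients total (25 patients per treatment arm" and "Stipulating a study power of 80% and an alpha level=0.05". Its rates are given as "with a baseline healing rate of 65% (with autogenous bone graft" and "we assume at 20% higher healing rate in BMP treated patients". Number of Sites/Investigators/Patients describes permuted blocks of even size within each centre, at up to 22 sites.

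**The concern.** A 2x2 table with 25 patients per arm has few possible outcomes. Fisher's test conditions on the total number of events, which makes the set of attainable p-values coarser still. Its real error rate therefore falls below the 0.05 that the plan allows, and real differences are missed without any extra protection being needed.

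Boschloo's test takes Fisher's p-value as its statistic and calibrates it over the unknown common rate. It makes the same promise, at most 5% whatever the common rate, and uses more of the allowance. With so few patients, power given up by the choice of test cannot easily be recovered elsewhere.

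**Working it through.** **Inputs.** From Sample Size Justification: 25 per arm, alpha 0.05, power 80%, control healing 65%, and a treatment rate 20 points higher (85%). Assumed: two-sided testing and independent binary outcomes. All rates other than 65% and 85% are illustrative, because the documents give none for infection or re-intervention.

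**The plan's own figures first.** The plan states "a non-inferiority margin of 20% our study will require at least 14 patients per treatment arm" and "If we stipulate our non-inferiority margin to be 10%, we will require 25 patients per group". Use n = (z₁₋α + z₁₋β)² × [p₁(1−p₁) + p₂(1−p₂)] / (difference + margin)² with one-sided alpha 0.05:

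- Numerator: (1.645 + 0.842)² × (0.2275 + 0.1275) = 6.18 × 0.355 = 2.19.
- Margin 20%: 2.19 / 0.40² = 13.7, so 14.
- Margin 10%: 2.19 / 0.30² = 24.4, so 25.

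Both match, which confirms 65% and 85% as the planning rates. Reading the 20% as relative (78%) would give 23 and 47. The 25 per arm is thus a non-inferiority figure. It says nothing about power for Fisher's test of equality.

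**Enumeration.** Let x and y be the event counts in arms of n₁ and n₂, and b the binomial probability.

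- Power(p₁, p₂) = sum of b(x; n₁, p₁) × b(y; n₂, p₂) over all rejected tables. Size is the same sum with p₁ = p₂, maximised over the common rate.
- Fisher rejects when its two-sided p ≤ 0.05.
- Boschloo rejects when Fisher's p ≤ c, with c the largest attainable value whose maximum size is ≤ 0.05.

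**Size at 25/25** (26 × 26 tables). Fisher's true size is 0.9% at a common rate of 10%, 2.2% at 20–25% and 2.6% at 35%. Its maximum is 3.28%, at 50%. For Boschloo c = 0.0792 and the maximum is 4.63%; the next attainable cutoff would give 5.14%. Boschloo rejects every table that Fisher rejects, plus 24 more. For example, 0 v 5 events gives Fisher p = 0.0502 and Boschloo p = 0.033; 2 v 8 gives 0.074 and 0.041.

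**Power at 25/25.**

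| Rates | Fisher | Boschloo | Gain (points) |
|---|---|---|---|
| 65% v 85% (plan) | 25.3% | 34.5% | 9.3 |
| 65% v 90% | 44.6% | 54.4% | 9.8 |
| 10% v 30% | 30.5% | 38.6% | 8.1 |
| 2% v 20% | 30.3% | 42.6% | 12.3 |
| 65% v 45% | 23.6% | 26.0% | 2.4 |
| 65% v 35% | 50.6% | 52.2% | 1.6 |

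Gains are taken before rounding. Over all rate pairs where Fisher has 20–80% power, the gain runs from 1.1 to 15.4 points, with median 7.7. At 65% v 85%, Fisher's test would need 31 per arm (34.7%) to match Boschloo at 25, which is 6 more per arm.

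**Dependence on the split.** The first rate belongs to the first arm.

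| Split | Fisher maximum size | Gain, 65% v 85% | Gain, 2% v 20% |
|---|---|---|---|
| 25/25 | 3.3% | 9.3 | 12.3 |
| 24/25 | 4.4% | 6.3 | 12.1 |
| 24/24 | 2.9% | 5.8 | 0.4 |
| 23/24 | 4.0% | 2.4 | 0.0 |
| 24/26 | 3.7% | 2.8 | 15.6 |
| 26/24 | 3.7% | 6.9 | 0.0 |
| 23/27 | 3.8% | 5.5 | 15.8 |
| 22/22 | 2.4% | 10.1 | 4.1 |

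With both arms within two of 25, the gain in the scenarios checked therefore runs from about 0 to 16 points. A wider imbalance can exceed that: 18.6 points for 2% v 20% at 22/28. In no case is it negative.

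**The case against.** The strongest reply is that nothing here is wrong. Fisher's test is conventional in small trials and controls error under the plan's alpha, and conditional against unconditional testing is a long-standing debate. That stands to this extent: the point concerns efficiency, and a reader who infers that the named test is invalid would be mistaken.

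The second reply is that the gain is erratic. A reader might take the 25/25 figures to mean that Fisher's test always forgoes some 8 to 12 points and never exceeds 3.3% error. The plan does not support that. Blocks run separately within up to 22 centres, so unfinished blocks can leave unequal arms. The sample size has no dropout allowance, so a single missing outcome changes the split. Fisher's maximum size is then up to 4.4% in the splits checked, and some gains vanish. Even at 25/25 only 44% of the rate pairs with 20–80% Fisher power gain 8 points or more. This limits the size of the claim but not its direction.

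Third, the inclusion criteria randomise the two legs of a bilateral fracture separately, so some outcomes may be correlated within a patient. Both tests assume independence, so this does not favour either.

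Last, Boschloo's test leaves power near 35% at the planning rates. That is correct, and the larger design question remains open.

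**Conclusion.** The point holds as an avoidable loss of efficiency. At the plan's own 65% v 85% with exactly 25 per arm, Boschloo's test gains about 9 points of power (25.3% to 34.5%) at a maximum error of 4.63%. Elsewhere the gain depends on the rates and the exact split, from nothing to about 16 points at splits near 25/25. What holds at every split is the ordering: error within 5%, and power never below Fisher's.

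This rests on two-sided testing at 0.05, independent binary outcomes, and 20% read as percentage points. The figures do not apply to variables with more than two categories.

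A reader might also infer that changing the test repairs the trial's power. It does not. The 25 per arm comes from a non-inferiority calculation with a 10% margin, while the stated null and the named test concern equality. For a two-sided test of 65% v 85%, the normal approximation needs about 73 per arm for 80% power. If union is analysed against a margin, neither test of equality answers that question, and this point applies only to the remaining binary outcomes.

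**What to change.** In Final Analysis, state before any comparative data are seen that between-group comparisons of equality on binary (2x2) outcomes, such as infection, need for further intervention and soft-tissue complications, will use Boschloo's unconditional exact test at two-sided 0.05. Keep Fisher's test for larger tables.

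State that tables are ordered by the two-sided Fisher p-value, since this is what ensures rejection whenever Fisher's test rejects. Doubling the one-sided version gives the same size and power at 25 per arm in every scenario checked. Report each risk difference with a matching unconditional exact confidence interval, and name the interval method.

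The cost is a sentence or two of wording. The test is in standard software, and no extra patients, visits or data are needed. It has to be prespecified: a switch made after seeing a Fisher p of 0.0502 would not be credible. The mismatch between the non-inferiority sample size and the test of equality needs its own correction.
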